10.5.2 Visit 2 (Day 2): Interim Visit

Visit 2 must occur the day after patient dosing. All treated household members will return for follow-up at Visit 2 only.

1. **Concomitant Medication:** Review the patient's use of any new or ongoing concomitant medications since the last visit.
2. **Adverse Events:** Patients will be questioned about any health status changes/AEs since last visit. All AEs will be recorded.
3. **Vital Signs:** The patient's vital signs will be recorded (pulse, blood pressure, temperature and respiration rate).
4. **Pregnancy Test:** A urine pregnancy test will be required of all female patients of childbearing potential.
5. **Louse Examination:** An Investigator or staff member, who is experienced and trained in detection and evaluation of head lice, will perform a visual inspection for the presence of live lice (i.e., live adults and/or nymphs). Louse examination should be conducted for 15 minutes or longer, unless any live lice are detected in less time. If any live lice are found during the exam, the patient should be discontinued and provided with alternative therapy. Duration of examination and number of live lice should be recorded in the patient's eCRF.
6. **Application Site Reactions:** Patients will be asked about any application site reactions since last visit (see Appendix A). Any reactions will be recorded.
7. **Ocular Irritation Assessment:** Patients will be questioned about any ocular discomfort resulting from contact with the study product. Any discomfort will be documented as an AE.
8. **Return Study Product:** Patients will return the used study product tube.
9. **Collect and Review Patient Diary:** Study staff will collect previously provided diary and review for compliance with the protocol.
10. **Provide Patient Diary:** A diary will be provided to record AEs and concomitant medications.

10.5.3 Visit 3 (Day 8 ± 2 days): Interim Visit

1. **Concomitant Medication:** Review the patient's use of any new or ongoing concomitant medications since the last visit.
2. **Adverse Events:** Patients will be questioned about any health status changes/AEs since the last visit. All AEs will be recorded.

CONFIDENTIAL PROTOCOL

A Randomized, Double-Blind, Placebo-Controlled, Parallel-Design, Multiple-Site Clinical Study to Evaluate the Therapeutic Equivalence and Safety of Ivermectin Lotion 0.5% (Actavis Laboratories UT, Inc.) to SKLICE® (ivermectin) Lotion, 0.5% (Arbor Pharmaceuticals, LLC) in the Treatment of Human Head Lice Infestation

3. **Vital Signs:** The patient's vital signs will be recorded (pulse, blood pressure, temperature and respiration rate).
4. **Pregnancy Test:** A urine pregnancy test will be required of all female patients of childbearing potential.
5. **Louse Examination:** An Investigator or staff member, who is experienced and trained in detection and evaluation of head lice, will perform a visual inspection for the presence of live lice (i.e., live adults and/or nymphs). Louse examination should be conducted for 15 minutes or longer, unless any live lice are detected in less time. If any live lice are found during the exam, the patient should be discontinued and provided with alternative therapy. Duration of examination and number of live lice should be recorded in the patient's eCRF.
6. **Application Site Reactions:** Patients will be asked about any application site reactions since last visit (see Appendix A). Any reactions will be recorded.
7. **Collect and Review Patient Diary:** Study staff will collect previously provided diary and review for compliance with the protocol.
8. **Provide Patient Diary:** A diary will be provided to record AEs and concomitant medications.

10.5.4 Visit 4 (Day 15 ± 2 days): End of Study

1. **Concomitant Medication:** Review the patient's use of any new or ongoing concomitant medications since the last visit.
2. **Adverse Events:** Patients will be questioned about any health status changes/AEs since the last visit. All AEs will be recorded.
3. **Vital Signs:** The patient's vital signs will be recorded (pulse, blood pressure, temperature and respiration rate).
4. **Pregnancy Test:** A urine pregnancy test will be required of all female patients of childbearing potential.
5. **Louse Examination:** An Investigator or staff member, who is experienced and trained in detection and evaluation of head lice, will perform a visual inspection for the presence of live lice (i.e., live adults and/or nymphs). Louse examination should be conducted for 15 minutes or longer, unless any live lice are detected in less time. Duration of examination and number of live lice should be recorded in the patient's eCRF.
6. **Application Site Reactions:** Patients will be asked about any application site reactions since last visit (see Appendix A). Any reactions will be recorded.
7. **Collect and Review Patient Diary:** Study staff will collect previously provided diary and review for compliance with the protocol.

CONFIDENTIAL PROTOCOL

A Randomized, Double-Blind, Placebo-Controlled, Parallel-Design, Multiple-Site Clinical Study to Evaluate the Therapeutic Equivalence and Safety of Ivermectin Lotion 0.5% (Actavis Laboratories UT, Inc.) to SKLICE® (ivermectin) Lotion, 0.5% (Arbor Pharmaceuticals, LLC) in the Treatment of Human Head Lice Infestation

10.6 Study Procedures

10.6.1 Informed Consent

At Visit 1, before performing any study-related procedures all patients will read and sign an IRB-approved ICF. In addition, patients who are considered minors in the state the study is being conducted (< 18 years of age in most states) must have a signed parental/guardian ICF, indicating approval to participate, as well as a signed assent to participate form, as appropriate. Patient's 11-17 years of age will read and sign an IRB-approved assent form and patients 6-10 years of age will provide verbal assent. Patients 6 months-5 years of age will be exempt from providing assent based on the child's comprehension and cognitive skills. If any other language is required, translation will be performed by a certified translator.

10.6.2 Medical History and Demographics

At Visit 1, each patient will be required to provide basic demographic information: date of birth, gender, ethnicity and race. Patients will also be questioned about medical history, including acute and chronic medical history and medical history relevant to their head lice.

10.6.3 Concomitant Medication

At Visit 1, patients will be questioned about current and previous medication use over the last four weeks. At all subsequent visits, patients will be questioned about ongoing or new concomitant medication use.

10.6.4 Adverse Events

At the end of Visit 1, patients will be questioned about any AEs that occurred during the visit. At Visits 2, 3, and 4 patients will be questioned regarding any changes in their medical status since their previous visit. Any significant changes observed after ICF/assent signing will be reported as AEs.

10.6.5 Vital Signs

The patient's vital signs will be recorded (pulse, blood pressure, temperature and respiration rate) at Visits 1, 2, 3, and 4.

10.6.6 Pregnancy Test

Urine pregnancy tests on females of childbearing potential will be performed at each visit. The test must be negative for the patient to be eligible for inclusion in the study. If the patient is of non-childbearing potential, the source document must list the reason why she is of non-childbearing potential (e.g., postmenopausal).

Any patient who becomes pregnant during the study must be discontinued and End of Study procedures completed. The outcome of the pregnancy will be followed by the Investigator to birth or early termination as appropriate. The pregnancy will be reported as an AE.

CONFIDENTIAL PROTOCOL

A Randomized, Double-Blind, Placebo-Controlled, Parallel-Design, Multiple-Site Clinical Study to Evaluate the Therapeutic Equivalence and Safety of Ivermectin Lotion 0.5% (Actavis Laboratories UT, Inc.) to SKLICE® (ivermectin) Lotion, 0.5% (Arbor Pharmaceuticals, LLC) in the Treatment of Human Head Lice Infestation

10.6.7 Louse Examination

The Investigator or other qualified staff will perform a visual inspection for the presence of live lice (i.e., live adults and/or nymphs) at each visit. Louse examination should be conducted for 15 minutes or longer, unless any live lice are detected in less time. Duration of examination and number of live lice should be recorded in the patient's eCRF. Patients with live lice present at Visits 2 or 3 should be discontinued from the study and provided with alternative therapy.

Determination of live lice can be aided by the use of a mild magnification (e.g., 5x).

10.6.8 Inclusion/Exclusion Criteria Review

At Visit 1, inclusion/exclusion criteria will be reviewed to ensure patients' eligibility for participation in the study.

10.6.9 Application Site Reactions

At Visit 1, the Investigator will grade the individual signs and symptoms (erythema, pyoderma, excoriation, pain, pruritus, edema) per Appendix A. This will serve as a baseline for subsequent assessments of application site reactions. At Visits 2, 3, and 4, application site reactions will be assessed by clinic staff. Reactions will be scored and recorded.

10.6.10 Ocular Irritation Assessment

At Visit 2, patients will be asked if the study product came into contact with their eyes. If contact is reported, they will be asked to report any signs or symptoms experienced. Any reported signs or symptoms should be recorded as AEs.

10.6.11 Dispense Study Product

[REDACTED]

10.6.12 Collect Study Product

Tubes of study product will be collected from all patients at Visit 2 and checked for compliance or evidence of tampering with the blind.

10.6.13 Provide Patient Diary

At Visit 1, patients will be provided with a diary to record the time and date of dosing, other concomitant medications and AEs, including any ocular discomfort.

At Visits 2 and 3, patients will be provided with a diary to record concomitant medications and AEs.

An adult member of the household will complete the diary for younger patients who are unable to complete the diary on their own.

10.6.14 Collect and Review Patient Diary

At Visits 2, 3, and 4, patient diaries will be collected and reviewed for compliance with the protocol.

CONFIDENTIAL PROTOCOL

A Randomized, Double-Blind, Placebo-Controlled, Parallel-Design, Multiple-Site Clinical Study to Evaluate the Therapeutic Equivalence and Safety of Ivermectin Lotion 0.5% (Actavis Laboratories UT, Inc.) to SKLICE® (ivermectin) Lotion, 0.5% (Arbor Pharmaceuticals, LLC) in the Treatment of Human Head Lice Infestation

10.7 Adverse Events

Patients will be encouraged to report signs, symptoms and any changes in health to the clinic staff. Severity of each AE will be determined based on observation and questioning of the patient. The Investigator will judge the severity and relationship of the event to the study products.

10.7.1 Adverse Event Definition

An AE is any untoward medical occurrence in a patient, regardless of whether it has a causal relationship with this treatment.

In this study, any AE occurring after the patient has signed the ICF/assent until the end of follow-up period should be recorded and reported as an AE.

An AE can, therefore, be any unfavorable and unintended physical sign, symptom, or laboratory parameter that develops or worsens in severity during the course of this study, or significant worsening of the disease under study or of any concurrent disease, whether or not considered related to the study product. A new condition or the worsening of a pre-existing condition will be considered an AE. Stable chronic conditions (such as arthritis) that are present before study entry and do not worsen during this study will not be considered AEs.

Accordingly, an AE can include any of the following:

- intercurrent illnesses
- physical injuries
- events possibly related to concomitant medication
- significant worsening (change in nature, severity, or frequency) of the disease under study or other pre-existing conditions drug interactions
- events occurring during diagnostic procedures or during any washout phase of this study
- laboratory or diagnostic test abnormalities that result in the withdrawal of the patient from the study, are associated with clinical signs and symptoms or a serious adverse event (SAE), or require medical treatment or further diagnostic work up, or are considered by the Investigator to be clinically significant (Note: Abnormal laboratory test results at the screening visit that preclude a patient from entering the study or receiving study treatment are not considered AEs.)

A treatment-emergent AE is any AE that occurs after initiation of study product, or any event already present that worsens in either intensity or frequency following exposure to study product.

10.7.2 Serious Adverse Events

An SAE is an AE, regardless of the relationship to study product, that results in any of the following outcomes or actions:

- Death

CONFIDENTIAL PROTOCOL

A Randomized, Double-Blind, Placebo-Controlled, Parallel-Design, Multiple-Site Clinical Study to Evaluate the Therapeutic Equivalence and Safety of Ivermectin Lotion 0.5% (Actavis Laboratories UT, Inc.) to SKLICE® (ivermectin) Lotion, 0.5% (Arbor Pharmaceuticals, LLC) in the Treatment of Human Head Lice Infestation

- A life-threatening AE (i.e., the patient was at immediate risk of death from the event as it occurred; does not include an event that, had it occurred in a more severe form, might have caused death)
- Inpatient hospitalization or prolongation of existing hospitalization means that hospital inpatient admission and/or prolongation of hospital stay were required for treatment of an AE, or that they occurred as a consequence of the event. Hospitalizations scheduled prior to study entry will not be considered SAEs, unless there was worsening of the pre-existing condition during the patient's participation in this study
- Persistent or significant disability or incapacity (refers to a substantial disruption of one's ability to conduct normal life functions)
- A congenital anomaly/birth defect
- An important medical event that may not result in death, be life-threatening, or require hospitalization, but may jeopardize the subject and may require medical intervention to prevent one of the outcomes listed in this definition. Examples of such events are intensive treatment in an emergency room or at home for allergic bronchospasm; blood dyscrasias or convulsions that do not result in hospitalization; or the development of drug dependency or drug abuse. Note: Any suspected transmission of an infectious agent via a medicinal product is considered an important medical event.

An AE that does not meet any of the criteria for seriousness listed above will be regarded as a non-serious AE.

10.7.3 Other Significant Adverse Events

When tested, marked haematological and other laboratory abnormalities (other than those meeting the definition of serious) and any events that led to an intervention, including withdrawal of test drug/investigational product treatment, dose reduction, or significant additional concomitant therapy, other than those reported as SAEs should be collected in the eCRF and summarized in the clinical study report.

10.7.4 Severity

The severity of each AE must be recorded as one of the choices on the following scales:

- Mild: No limitation of usual activities
- Moderate: Some limitation of usual activities
- Severe: Inability to carry out usual activities

10.7.5 Relationship of an Adverse Event to the Study Drug

Adverse events will be assessed for the relationship to the study product (causality) according to the following scale:

CONFIDENTIAL PROTOCOL

A Randomized, Double-Blind, Placebo-Controlled, Parallel-Design, Multiple-Site Clinical Study to Evaluate the Therapeutic Equivalence and Safety of Ivermectin Lotion 0.5% (Actavis Laboratories UT, Inc.) to SKLICE® (ivermectin) Lotion, 0.5% (Arbor Pharmaceuticals, LLC) in the Treatment of Human Head Lice Infestation

TERM	DEFINITION	CLARIFICATION
No Reasonable Possibility (not related)	This category applies to those AEs which, after careful consideration, are clearly due to extraneous causes (disease, environment, etc.) or to those AEs, which after careful medical consideration at the time they are evaluated, are judged to be unrelated to the test drug.	An adverse experience may be considered No Reasonable Possibility if it is clearly due to extraneous causes or when (must have two): It does not follow a reasonable temporal sequence from the administration of the test drug. It could readily have been produced by the patient's clinical state, environmental or toxic factors, or other modes of therapy administered to the patient. It does not follow a known pattern of response to the test drug. It does not reappear or worsen when the drug is re-administered.
Reasonable Possibility (related)	This category applies to those AE for which, after careful medical consideration at the time they are evaluated, a connection with the test drug administration cannot be ruled out with certainty or felt with a high degree of certainty to be related to the test drug.	An adverse experience may be considered Reasonable Possibility related if or when (at least two of the following): It follows a reasonable temporal sequence from administration of the drug. It could not be reasonably explained by the known characteristics of the patient's clinical state, environmental or toxic factors, or other modes of therapy administered to the patient. It disappears or decreases on cessation or reduction in dose. There are important exceptions when an AE does not disappear upon discontinuation of the drug, yet drug-relatedness clearly exists. It follows a known pattern of response to the test drug.

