10.4 Treatments

10.4.1 Treatments Administration

Patients will be provided with verbal and written instructions on how to administer the study product at home. At Visit 1, eligible patients will receive a 4 oz (117 g) tube of randomized study product (i.e., Test, Reference or Placebo). Study product should be applied on the day of or the day after enrollment into the study. The day of dosing will be considered Day 1. Patients, infested household members, and/or caregivers will be instructed to apply the study product to dry hair in an amount sufficient (up to 1 tube) to thoroughly coat the hair and scalp, avoiding contact with the eyes. Study product should be left on the scalp for 10 minutes before rinsing with water only. Patients should wash their hands after application of the study product. Hair should be allowed to dry naturally (pat drying with decontaminated towel is permitted) and left uncovered after application of the study product. Following application and rinsing of the study product, patients may not shampoo, wash, or rinse their hair or scalp until the Day 2 visit has been completed.

If any non-infested household member is pregnant or lactating at the time of the study, this person may not be involved with application of the study product to any household members.

The study product should be applied as a single dose. Patients should not use the product more than once. Tubes of study product will be collected at Visit 2 and the site will verify the product was used and rinsed. If a patient inadvertently does not return a tube of study product at its respective return visit, the patient should be instructed to return it as soon as possible or at the next visit.

On Day 1, before applying treatment, all bedding, hats, clothing, and towels used by infested persons or their household, sexual, and close contacts in the two days before treatment should be decontaminated by machine washing in high temperatures (at least 150°F) and drying in a hot dryer for at least 20 minutes (additional time should be added if large loads are dried). Clothing or items that are not washable can be dry-cleaned or sealed in a plastic bag and stored for two weeks. Personal care items such as combs, brushes, and hair clips should be washed in hot water (at least 135°F) for 10 minutes. Instructions on good hygiene and proper methods of decontamination will be provided to the patient and caregivers.

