8.3.1 Adverse Events

All the adverse events (AEs) reported throughout the study will be coded and classified according to the MedDRA (Medical Dictionary for Regulatory Activities) coding dictionary (Version 20.0 or higher). Each adverse event is to be evaluated for date of start and end, seriousness, severity, causal relationship with the study drugs, action taken and outcome.

The total number and percentage of patients with at least one AEs, discontinued study drug due to AEs, AE severity and AEs related to investigational product, serious AEs and death will be summarized by treatment groups.

A summary table of the number and percent of patients with AEs by system organ class, preferred term, and treatment group will be presented. Each patient will be counted only once within each preferred term.

A frequency summary table of the number of AEs by system organ class, preferred term, severity, and treatment group will be presented. Severity will be classified as “Mild”, “Moderate”, or “Severe”.

Similarly, a frequency summary table of the number of AEs by system organ class, preferred term, and relationship to a study drug, and treatment group will be presented. Relationship to a study drug will be classified as “Related” or “Not Related”.

Adverse event frequencies will be compared between treatments using Fisher’s exact test. If the overall Fisher’s test is statistically significant, a pairwise test will be conducted for Test and Reference to determine if the difference in AEs is related to the active product.

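### The causality table in Protocol 10.7.5 counts two items that cannot discriminate after a single application, so some adverse events can be coded either way (minor)

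*Protocol*

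**What the plan says.** The table in Protocol 10.7.5 has a definition and a clarification for each of two categories.

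- **No Reasonable Possibility (not related).** The clarification allows this category "if it is clearly due to extraneous causes or when (must have two" of four items). The items are: implausible timing; a ready explanation in the patient's condition, environment or other treatment; no match to a known response pattern; and "It does not reappear or worsen when the drug is re-administered".
- **Reasonable Possibility (related).** "An adverse experience may be considered Reasonable Possibility related if or when (at least two of the following"). Three of the items are the counterparts on timing ("It follows a reasonable temporal sequence from administration of the drug"), alternative explanation and known pattern. The fourth is "It disappears or decreases on cessation or reduction in dose", with a note that there are important exceptions.

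On dosing, Protocol 10.4.1 says: "The study product should be applied as a single dose. Patients should not use the product more than once". It also says: "Study product should be left on the scalp for 10 minutes before rinsing with water only".

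On use of the result, SAP 8.3.1 says: "Relationship to a study drug will be classified as “Related” or “Not Related". The split appears in shells T16.1.9.9 and T16.1.9.12, which offer no third category. Protocol 10.7.7 has the relationship recorded by reference to this scale, as the investigator judges it.

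**The concern.** The table fits a drug that is given repeatedly and can be stopped, reduced or restarted. Here, if the protocol is followed, there is no re-administration and no dose reduction, and cessation is the rinse-off on Day 1 for every patient. One of the four items on each side therefore carries no information about cause, yet it can supply half of the score needed. The table does not say how to score an item that cannot be observed.

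The re-administration item is the more awkward of the two. Nothing can reappear on a re-administration that never happens, so a literal reader may tick it for every event. One further item then suffices for not related. An event with plausible timing and a known pattern could be set aside because another cause is also available.

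At stake is consistency between sites in the related-event tables, and in follow-up. Protocol 10.11 asks for every effort to follow related events to a final outcome, while 10.7.7 lets monitoring of an event stop once an unrelated cause is determined.

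**Working it through.** There is no planned figure to reproduce, so the check enumerates the two rules.

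**Inputs**, all from Protocol 10.7.5 except the last:
- four items per side, threshold two on each side;
- three items that appear on both sides in near-mirror form: timing (T), no other adequate explanation (E), known pattern (K), each scored 1 if it points to the drug;
- one unpaired item per side: D = 1 if the cessation item is counted as met, N = 1 if the re-administration item is counted as met;
- one application per patient (10.4.1), which is why D and N cannot be informative.

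**Rules.** Let s = T + E + K. If the three pairs are treated as exact opposites:
- related if s + D ≥ 2;
- not related if (3 − s) + N ≥ 2, that is, s ≤ 1 + N.

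The 2 × 2 × 2 = 8 profiles split as 1, 3, 3 and 1 for s = 0, 1, 2 and 3.

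| Reading | Both tests met when | Both | Related only | Not related only |
|---|---|---|---|---|
| Neither item counts (D = 0, N = 0) | s ≥ 2 and s ≤ 1 | 0 of 8 | 4 | 4 |
| Only re-administration counts (D = 0, N = 1) | s = 2 | 3 of 8 | 1 | 4 |
| Only cessation counts (D = 1, N = 0) | s = 1 | 3 of 8 | 4 | 1 |
| Both count (D = 1, N = 1) | s = 1 or 2 | 6 of 8 | 1 | 1 |

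**Benchmark.** If D and N were observable and free to vary, as with repeated dosing, the four rows together give 0 + 3 + 3 + 6 = 12 of 32 profiles meeting both tests. That is 37.5%, the same share as 3 of 8.

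**Are the pairs exact opposites?** Timing and known pattern are. Explanation is not: one side asks whether another cause could readily have produced the event, the other whether no other cause could reasonably explain it. An event may be reasonably but not readily explained, and then it scores on neither side. Allowing that middle state gives 2 × 2 × 3 = 12 profiles. With D and N not counted, an event in the middle state with plausible timing but no known pattern scores 1 on each side and meets neither test; so does its reverse (implausible timing, known pattern). So 2 of 12 profiles fall in no category and the other 10 fall in exactly one. Dropping the two items removes the overlap but leaves a small gap that a rule must close.

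**The case against.** The best defence is that the table guides judgement and is not a scoring algorithm. The clarifications say an event may be considered in a category. The definitions rest on medical consideration, and related includes any event whose link to the drug cannot be excluded with certainty. Section 10.7.7 leaves the call to the investigator. A trained investigator would probably treat the re-administration item as not applicable, which gives 0 of 8. This stands. It means the plan is not without a governing principle, and that the likely result is uneven coding, with no forced double entry.

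Two stronger readings are tempting, and the documents support neither. A reader might infer that most adverse events will satisfy both sides. The 6 of 8 figure needs both items to be read generously. The cessation item is not met by every event that resolves: one that starts days after rinse-off and later clears did not disappear on cessation. The profiles are also equally weighted logical combinations, and the documents give no frequencies for them. A reader might also infer that single dosing causes the overlap. The 12 of 32 benchmark shows that two permissive two-of-four lists overlap with repeated dosing as well. What single dosing adds is that one item on each side has no content.

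The impact is also limited. All events are recorded whatever their judged relationship (10.7.7). Serious events are reported regardless of causality (10.7.8, 12.2.9). The planned Fisher comparison concerns event incidence (SAP 8.3.1, T16.1.9.10), and the relationship shells carry no p-value. Ordinary lice symptoms are not adverse events unless they worsen to a clinically significant extent (Protocol 11.8), which narrows the obvious example of itching. Section 10.11 requires follow-up of any event unresolved at the last visit, related or not. All of this stands and lowers the weight of the point. It does not explain why the table should keep two items that the design cannot test.

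**Conclusion.** The point holds as a minor one. Two items in the causality table do not fit a single-application trial. Read literally, the rule lets an event be called not related on one informative criterion and lets some events meet both tests: 3 of 8 profiles if only the re-administration item counts, up to 6 of 8 if both count, 0 of 8 if neither does. These counts treat the paired items as exact opposites and say nothing about how often such events will occur.

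The consequence is possible inconsistency in the descriptive Related / Not Related tables and in follow-up of related events. Assessors are blinded and the rule is the same in every arm, so noise is to be expected, with no built-in advantage for one product. Comparisons of event incidence, reporting of serious events, and the equivalence and superiority analyses are unaffected.

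**What to change.** In the Protocol 10.7.5 table:
1. Mark the re-administration item and the cessation or dose-reduction item as not applicable because of the single application, and as not counting toward the two.
2. Keep the threshold of two, applied to the remaining three items on each side. The separate route for a clearly extraneous cause can stay as it is.
3. State that an event whose item counts meet both sides, or neither side, is recorded as Reasonable Possibility. This follows the table's own definition of related and closes the gap left by the inexact explanation pair.

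The cost is a wording change and a line in site training or the adverse-event form guidance. The SAP categories and shells stay as they are. The downside is that slightly more events may be classed as related, with the follow-up that Section 10.11 attaches to them.
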